## Evaluating the Impact of an Emotion Regulation Intervention on Emotion Perception

### Purpose of the Study

**Aim 1:** To evaluate the short-term impacts of an emotion regulation intervention on emotion perception in the laboratory. In the laboratory training session, we will compare performance on behavioral emotion perception tasks between participants who receive the intervention, a training in an emotion regulation skill (i.e. mindful breathing), and participants in the control conditions (perspective-taking and worry inductions). **Hypothesis 1:** We predict that participants in the emotion regulation intervention condition will show less negative bias in their performance compared to participants in the control conditions. We also predict that intensity of emotional distress will be associated with negative biases.

**Aim 2:** To investigate the longitudinal effects of this intervention on emotion perception outside the lab using experience sampling. After the laboratory training session in aim 1, participants in both groups will receive an auditory reminder of the emotion regulation skill (a specific tone) three times a day through their mobile phones for one week and then will complete emotion perception tasks. Using our method of generalization, the participants in the intervention group have learned to associate the tones with reductions in emotional distress. For this aim, we will compare changes in performance on the emotion perception tasks over time between the three groups. **Hypothesis 2:** We predict that these cues will lead to greater decreases in negative biases in emotion perception over time compared to the control conditions. We will also test whether changes in emotional distress and regulation mediate the longitudinal changes in emotion perception performance.

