Mindfulness is a promising emotional regulation skill that could reduce negative biases in emotion perception. Identifying a brief intervention that effectively reduces negative emotions is necessary to investigate the impact of emotion regulation on emotion perception. Previous research has shown that mindfulness is a skill that is positively associated with both emotion perception ability and emotion regulation (Quaglia, Goodman, & Brown, 2015). First, mindfulness can be used to modulate experiences of negative emotions (Chambers, Gullone, & Allen, 2009; Roemer, Williston, & Rollins, 2015). For example, one study found that a 15-minute mindful breathing induction led to less negative emotional responses to negatively-valenced stimuli than control condition (a worry induction) (Arch & Craske, 2006a). Secondly, brief mindful breathing interventions can also lead to improvements in emotion perception. (Tan, Lo, & Macrae, 2014) Taken together, findings suggest that mindful breathing can be used as an emotion regulation skill that may have beneficial impacts on emotion perception. To our knowledge, these relationships have yet to be tested within clinical samples with emotion dysregulation. Given its established effect on emotion regulation, a mindful breathing skill will be taught to participants as an emotion regulation skill as a micro-intervention. A useful comparison condition would be a micro-intervention that targets perspective-taking (Jackson, Meltzoff, & Decety, 2005), another social cognitive process related to perceiving other people's emotions. Perspective-taking inductions may share similar mechanisms as mindfulness as another type of metacognitive intervention, but they do not address dysregulated emotions. Therefore, a perspective-taking micro-intervention will be used in this study as the active comparison condition.

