Specific Aim 1: Aim 1 will determine if the emotion regulation intervention leads to fewer negative biases in emotion perception during the laboratory training session. For this aim, we will conduct ANCOVA analyses to study group differences in performance on the emotion perception laboratory tasks, controlling for their baseline scores assessed in the intake session. To compare the conditions' impacts on negative biases, we will analyze group differences in 1) number of trials with neutral facial expressions are misclassified as negative emotions; 2) accuracy for positive emotions and negative emotional expressions. We will also examine the relationship between emotional distress and emotion perception. Hypothesis 1: Participants in our emotion regulation condition will have less negative bias in emotion perception (e.g. fewer neutral faces misclassified as negative, lower accuracy for negative emotions, higher accuracy for positive emotions) compared to participants in both the control conditions. Even though the perspective-taking and mindful breathing conditions may have similar effects (e.g. increasing attention to social cues (Olsson et al., 2016; Quaglia, Goodman, & Brown, 2016)), perspective-taking inductions may still lead to mood-congruent biases by increasing negative emotional responses (Lamm, Batson, & Decety, 2007). Therefore, we predict that the emotion regulation intervention would reduce this bias significantly more than both the worry and perspective-taking conditions. We also predict that intensity of emotional distress will be related to negative biases in emotion perception.

Specific Aim 2: Aim 2 will compare the changes in emotion perception over time between the emotion regulation breathing condition and the control conditions. For this aim, Multilevel modeling (MLM) will be used because it permits evaluation of longitudinal data on participants over time with trajectories for each participant examined as random effects. We will conduct MLM analyses to study group differences in changes in the laboratory emotion perception tasks assessed during intake (time 1), the training session (time 2) and after the testing phase (time 3). For the phone-based behavioral task, we will first examine the psychometric properties of this measure in this clinical sample. Then, we will analyze group

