differences in the valence of emotion perception ratings over the one-week testing phase. We will also examine whether changes in emotion dysregulation and distress mediate changes in negative biases over time. Finally, we will also explore the effects of the intervention on self-reported psychological and social functioning. Hypothesis 2: One week of hearing the tones via mobile phones will lead to greater long-term changes in negative biases emotion perception for participants in the emotion regulation condition compared to the participants in the control conditions. Changes in emotional regulation and distress over time will mediate changes in negative biases in emotion perception over time.

If our hypotheses are not supported and the conditions do not have significantly different effects on emotion perception, these findings would be indicative of trait-like deficits in emotion perception beyond the momentary effects of mood or perspective-taking. We would then use moderation analyses to explore the role of other stable factors within emotion perception performance, such as trait empathy (measured by the IRI) or psychiatric diagnoses.

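### The comparators named in Hypothesis 1 (worry and perspective-taking) are not the arms the protocol randomises, and the tone-naive description of the control conditions does not fit Habituation

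*Combined protocol and SAP*

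**What the plan says.** **Hypotheses and rationale.** Purpose of the Study, Aim 1, compares the intervention with "participants in the control conditions (perspective-taking and worry inductions". Background & Significance says that "a perspective-taking micro-intervention will be used in this study as the active comparison condition", and its closing summary says both comparison inductions have been shown to raise distress under stress. Potential Benefits calls the control condition the worry induction and the active comparison group the perspective-taking induction. In Data Analysis & Statistical Considerations, Hypothesis 1 is first put generally, "compared to participants in both the control conditions", and then specifically: "Therefore, we predict that the emotion regulation intervention would reduce this bias significantly more than both the worry and perspective-taking conditions". If the conditions do not differ, the section says "these findings would be indicative of trait-like deficits in emotion perception beyond the momentary effects of mood or perspective-taking".

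**Arms and procedures.** Design & Procedures (Study Overview) randomises to Mindful Breathing, Habituation and Control, and Experimental Procedures describes exactly those three. Control receives the stressor task with no added instructions and hears no tone in training. Habituation follows the team's previous generalisation study.

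**The tone.** For Mindful Breathing and Habituation alike, a tone sounds once skin conductance is back at baseline, and the same sentence says participants learn by classical conditioning to link it with reduced arousal and distress. The Testing Phase text says participants in the control conditions (plural) hear the tone with no earlier association to it, as a check on placebo effects. Aim 2 rests on the premise that "the participants in the intervention group have learned to associate the tones with reductions in emotional distress".

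**Hypothesis 2.** The analysis section says "Aim 2 will compare the changes in emotion perception over time between the emotion regulation breathing condition and the control conditions", and predicts greater change "compared to the participants in the control conditions".

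**The concern.** A hypothesis needs comparators that the design creates. Neither induction named in Hypothesis 1 is delivered by any described procedure, and no section says where Habituation sits in the hypotheses. Three things follow.

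- **Rationale.** Breathing was expected to beat both comparators because they raise distress. Background & Significance reports that habituation reminders lowered distress and arousal more than a control condition in the team's earlier study.
- **Null-result reading.** A null finding would be interpreted as evidence about perspective-taking, which no described arm manipulates.
- **Role of the tone in Hypothesis 2.** The tone is what the phones deliver. If Habituation counts as a control, one control arm is tone-trained and the other tone-naive, so only Control can play the placebo role given to both.

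At stake is what a result may be said to show, and whether the comparisons are settled before the data are seen.

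**Working it through.** **1. The sections side by side**

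| Item | Purpose, Background, Benefits, Analysis | Study Overview, Experimental Procedures |
|---|---|---|
| Active comparator | Perspective-taking | Habituation |
| Other comparator | Worry induction | Stressor task only |
| Expected effect on distress | Both raise it | Habituation reminders lowered it in the earlier study (Background); nothing stated for Control |
| Tone pairing in training | Attributed to the intervention group | Mindful Breathing and Habituation; not Control |

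This is more than relabelling. A stressor with no further instructions is not a worry induction, and Condition 2 has no perspective-taking content.

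**2. Who the control conditions are.** Aim 1 uses the plural for both comparators, the general form of Hypothesis 1 says both, and the Testing Phase text is also plural. Experimental Procedures calls Habituation a comparison condition. Counting Habituation as part of the intervention does not work: Aim 2 identifies the emotion regulation condition with breathing, and its manipulation check asks about the breathing skill. So Habituation falls among the controls, and the no-prior-association statement is then true of Control only.

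**3. The plan's own power figure.** Inputs from Data Analysis & Statistical Considerations: 3 groups, N = 72 (24 per group), f = 0.38, alpha 5%.

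- Noncentrality = N × f² = 72 × 0.1444 = 10.40, with 2 and 69 degrees of freedom.
- Omnibus F power = 81.3%, against a stated minimum of 80%. The figure reproduces. The fault is in the definition of the arms, not in the arithmetic.

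**4. Illustration: power to beat both comparators.** My assumptions, not in the documents: one time point, no baseline covariate, pooled error on 69 degrees of freedom, and two-sided 5% tests counted in the predicted direction. The standard error of a pairwise difference is √(2/24) = 0.289 SD. Single-contrast power is from the noncentral t; power to beat both is by simulation.

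Breathing against two equal comparators: d = 0.38 × 3/√2 = 0.81. With Habituation midway, there are two ways to set the scale:

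- Hold breathing versus Control at d = 0.81. Breathing versus Habituation is then 0.40, and f falls to 0.33.
- Hold f = 0.38. Breathing versus Control is then 0.38 × √6 = 0.93, and breathing versus Habituation is 0.47.

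| Habituation's share of the benefit on bias | Versus Control | Versus Habituation | Beat both |
|---|---|---|---|
| None | 79% | 79% | 67% |
| Half, d = 0.81 held | 79% | 28% | 26% |
| Half, f = 0.38 held | 89% | 36% | 35% |
| All | 79% | 2.5% | 2.5% |

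The first and last rows are the same under either scaling. The planned baseline covariate would raise power where a true difference exists, but the documents give no correlation for it. For the three-time-point multilevel model of Hypothesis 2 the table is no more than a rough guide.

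**The case against.** **The arms are clear and the models run.** This stands. ANCOVA and the multilevel model can be fitted to the three randomised groups, and the general form of Hypothesis 1 is testable on them. A reader might infer that Hypothesis 1 is untestable altogether. The documents do not support that: only the specific prediction, its rationale and the null-result reading fail to fit.

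**Control conditions might mean the tone-naive arm alone.** The Testing Phase sentence would then be true. The label control condition is attached to arm 3 only, and the same text speaks of both conditions in a three-arm study, which suggests wording carried over from another design. This is why the tone point is conditional. The plural in three places still favours the wider reading.

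**Breathing and Habituation are not identical.** This is right. Only Mindful Breathing pairs the tone with a taught skill, and Aim 2 also calls the tone a reminder of that skill. Presentation counts differ too: 2 to 4 per stressor for Habituation, against three in the general stressor description. The overlap is in the learned link between tone and reduced distress, not in everything the arms receive.

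**Pooling.** A reader might infer from the wording of Hypothesis 2 that the two controls are to be pooled, so that a significant pooled result could pass for superiority over Habituation. No section proposes pooling; Aim 2 speaks of comparing three groups. Nor would a gap between a pooled and a both-comparators reading depend on Habituation working: even with no Habituation effect, power is 89% pooled against 67% for both.

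**Habituation may do nothing to bias.** It may. The earlier study is cited for distress and arousal only. The textual conflict does not depend on this; only the illustrative power does.

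**Conclusion.** The contradiction is in the text and needs no assumption. Five sections or statements name worry and perspective-taking as comparators, the randomised arms are Habituation and a stressor-only Control, and no procedure delivers either named induction. The specific prediction in Hypothesis 1, the distress-raising rationale and the reference to perspective-taking in the null-result reading do not fit the arms described.

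On the reading the plural supports, the statement that the controls have no earlier association with the tone is false for Habituation. The tone-distress association that Hypothesis 2 relies on then does not separate breathing from Habituation, although the taught skill still does.

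The sample size arithmetic is sound. The consequence for power is uncertain: from 67% down to 2.5% to beat both comparators, depending on an effect of Habituation on bias that the documents do not give. Which set of arms is intended cannot be decided from the text. The procedures figure in the Study Overview was not available to me; it might show the intention but would not remove the conflict.

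**What to change.** Reconcile Purpose of the Study, Background & Significance, the Testing Phase text, Potential Benefits and the analysis section with the Study Overview and Experimental Procedures, before outcome data are examined.

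If the randomised arms stand:

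1. Restate Hypotheses 1 and 2 as two prespecified contrasts: Mindful Breathing versus Control, and Mindful Breathing versus Habituation. For the claim in Hypothesis 1 against both, require each test to succeed at 5%.
2. Limit the no-prior-association statement and the placebo-control role to Control.
3. Remove perspective-taking from the interpretation of a null result.

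If worry and perspective-taking are the intended arms, the Study Overview and Experimental Procedures must be reconciled to describe them and how the tone is handled in each.

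**Cost.** In the first case, wording only: no extra participants or visits. The drawback is that the contrast with Habituation may have power well below the stated 80%, which the plan should acknowledge. In the second case, new procedure text and its review are needed. A Habituation versus Control contrast, and a statement of the confidence interval width for breathing versus Habituation, would be useful but are optional and not part of the error.

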(3) A phone-based assessment of emotion perception, adapted from procedures used in text-based emotion perception research in healthy populations (Cheshin, Rafaeli, & Bos, 2011). Participants receive standardized text messages that are previously rated for emotional valence on a 0 (very negative) to 9 (very positive) scale by independent raters. To increase ecological validity, participants are told that these messages have been sent by the experimenter, who is expressing an emotion through the message (e.g. "I just got into an argument with a friend, so I'm not having a good day"). After participants receive the text message, they are instructed to rate the valence of the emotion of the message on the same 10-point scale. This phone-based emotion perception task will only be administered during the one-week testing phase. See the text message script document for the text message content participants would receive during testing phase.

Emotion: Emotional arousal will be measured through self-report and physiological measures: (1) Skin conductance will be measured using Ag-AgCl electrodes, which are connected to a Biopac MP150 device in an adjacent room. Amplified signals of analog data are converted to digital form and filtered using Biopac's Acqknowledge Software and are stored in a database on the computer. (2) Subjective units of general psychological distress (SUDS; visual analogue scale from 0-100); (3) the Sedation Scale (SS), a self-report measure of emotional and general levels of arousal, and (4) the PANAS-2 (Watson, Clark, & Tellegen, 1988), a measure of current emotional state.

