## Data Analysis & Statistical Considerations

For the primary outcome of biases in emotion perception, the estimates were derived from a mean difference between conditions. With a Type-I error rate of 5% and 72 participants (24 per group), we will have at least 80% power to detect a medium to large effect size (Cohen's  $f = 0.38$ ), based on previous research demonstrating negative biases in emotion perception using similar behavioral measures. (Schmid & Schmid Mast, 2010) Because we anticipate a 10% to 15% rate of dropout, 30 participants will be randomized to each group. Therefore, this study will recruit 90 adult participants over the age of 18 who have high emotion dysregulation and interpersonal problems.

Since 2004, the CBTRP has recruited a range of adult psychiatric samples all characterized by problems with emotion regulation. Across studies of emotional functioning, it is estimated that our lab has run over 980 participants since 2004, at a rate of roughly 90 per year. In our previous NIMH project, over 33 months we have screened 1154 individuals and enrolled 169 participants, at a rate of 5.12 per month. We project enrolling 90 participants over 14 months, at a rate of 6.43 per month. Given our demonstrated track record of success meeting the required recruitment target in the present application, we expect to meet recruitment targets in the proposed project.

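### The phone-task analysis, as worded, leaves out each message's independent pre-rating, so message content adds noise and, if the message mix differs by arm, biases the group contrast

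*Combined protocol and SAP*

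**What the plan says.** Measures and Tasks (phone-based assessment) describes "standardized text messages that are previously rated for emotional valence on a 0 (very negative) to 9 (very positive) scale by independent raters". Participants then "rate the valence of the emotion of the message on the same 10-point scale". The task is given only in the testing week, so it has no baseline.

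Experimental Procedures (Testing Phase) sets three prompts a day for one week. A participant who reports SUDS above 2 receives the tone, reports distress again and rates a message. Otherwise the participant gets a thank-you text and rates nothing.

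Data Analysis & Statistical Considerations (Specific Aim 2) first calls for a look at the task's psychometric properties, without saying what that will produce. It then plans to compare group "differences in the valence of emotion perception ratings over the one-week testing phase". It names no deviation from the pre-rating, no message covariate and no message random effect. Hypothesis 2, in the same section, concerns negative biases.

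**The concern.** A negative bias means reading a message as more negative than it is, and the pre-rating supplies that reference point. For the face task, Specific Aim 1 scores responses against the emotion shown. For the phone task, the planned comparison has no such reference, so a low mean rating can reflect negative messages or negative perception.

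This would matter little if everyone rated the same messages. The distress gate, together with ordinary non-response, makes that unlikely. The intervention is also meant to lower distress, so the gate may open at different rates in the three arms. Background & Significance reports that phone reminders in the earlier study reduced distress against placebo sounds. Two things are at stake: precision in all cases where rated sets differ between people, and validity of the contrast if the message mix differs between arms.

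**Working it through.** **The plan's own figure.** The power statement concerns the primary bias outcome: 72 participants, 24 per group, f = 0.38, alpha 5%. For the omnibus F test with 2 and 69 df, the noncentrality is 72 × 0.38² = 10.4 and power is 81.3%. This agrees with "we will have at least 80% power to detect a medium to large effect size". For dropout ("we anticipate a 10% to 15% rate of dropout"), 72/0.90 = 80 and 72/0.85 = 84.7, so 85. The plan that "30 participants will be randomized to each group" covers both. No figure is given for the phone task.

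**Inputs from the documents.** Ratings and pre-ratings on the same 0 to 9 scale; at most 3 × 7 = 21 prompts; 24 per arm.

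**Assumed inputs (not in the documents).** Person SD 0.7; residual SD 1.5; SD of message valence s_m = 1.5 to 2.5; k rated messages per person; ratings follow the pre-rating with slope 1; pre-ratings free of error.

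**Variance of a person's mean rating**
- Message content removed: V_adj = 0.7² + 1.5²/k
- Content left in, k messages from a common set of 21: V_raw = V_adj + (s_m²/k) × (21 − k)/20
- Content left in, messages drawn independently for each person: V_raw = V_adj + s_m²/k
- Difference between two arms detectable with 80% power (two-sided 5%, normal approximation): 2.8 × √(2V/24)

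At k = 7, V_adj = 0.490 + 0.321 = 0.811. With a common set, the added term is (2.25/7) × 0.7 = 0.225 up to (6.25/7) × 0.7 = 0.625, so V_raw is 1.036 to 1.436. With independent draws, the added term is 0.321 to 0.893, so V_raw is 1.133 to 1.704.

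| k | Message set | V_raw / V_adj | Detectable difference, adjusted | Detectable difference, unadjusted |
|---|---|---|---|---|
| 7 | common 21 | 1.28 to 1.77 | 0.73 | 0.82 to 0.97 |
| 14 | common 21 | 1.09 to 1.24 | 0.65 | 0.68 to 0.73 |
| 21 | common 21 | 1.00 | 0.62 | 0.62 |
| 7 | independent draws | 1.40 to 2.10 | 0.73 | 0.86 to 1.06 |

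**Other SDs.** With person SD 0.7 and residual SD 1.0, or 1.0 and 1.5, message SD 1.5 to 3.0, and 5 to 15 rated messages, the ratio runs from 1.04 (common set) to 3.6 (independent draws).

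**When does the contrast become biased?** Simulated pairwise comparisons used 24 per arm, person SD 0.85, residual SD 1.25, message SD 2.5, 21 messages and 2,000 trials per scenario. The adjusted analysis here subtracts the pre-rating, with true slope 1.
- All 21 rated by everyone: identical results; power 87% for both at a true difference of 0.8.
- 10 of 21 chosen at random per person: no bias; power 68% unadjusted against 81% adjusted.
- Random choice, 7 rated in one arm and 14 in the other, no true difference: 5% rejections either way. Unequal counts alone do not bias the contrast.
- One fixed order, one arm rating the first 7 and the other the first 14, no true difference: 44% rejections unadjusted against 5% adjusted. This is an extreme case, averaged over possible orders.

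More simply, if arms differ by 10 percentage points in the share of positive messages, and positive and negative messages lie 4 to 6 points apart, the unadjusted contrast shifts by 0.10 × 4 = 0.4 to 0.10 × 6 = 0.6 points with no difference in perception.

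**Subtraction or covariate?** Subtraction fixes the slope at 1. If the true slope were 0.7, as could happen when ratings of extreme messages shrink toward the middle, the difference score would keep 0.3² = 9% of the message variance and the unadjusted rating 0.7² = 49%. At k = 7 with independent draws, the variance ratio of unadjusted to subtracted scores is then 1.15 (0.969/0.840) to 1.40 (1.249/0.892), not 1.40 to 2.10.

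**The case against.** The plan never says that unadjusted ratings will be used. Its sentence is a short summary, Hypothesis 2 speaks of bias, the pre-ratings are on the right scale and a psychometric step comes first, so the team may intend a bias score. That is fair as to intent. It does not help the analysis as written, because no bias score or message term is defined anywhere.

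The messages are also standardised, and the script is a separate document not available here. If everyone rated the same 21, nothing would be lost. This stands, and it limits the size: a reader might infer a loss even at 21 rated messages, but that needs independent draws from a larger pool or different sets per person, and the documents describe neither.

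A reader might also infer that the phone contrast is biased. The documents do not support that. They do not say how messages are assigned, and if assignment is independent of arm and of the gate, only precision suffers.

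Finally, no power is claimed for the phone task, and its measurement properties are still to be examined. That bears on priority, not on whether the analysis should use a value already held.

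**Conclusion.** The concern holds for the phone-task analysis as worded: it omits a reference value that exists for every message, in a design where the rated messages will probably differ between people. The loss of precision is moderate when few messages are rated. Under the assumed SDs and a common set of 21, the variance of a person's mean is 1.28 to 1.77 times larger at 7 rated messages (detectable difference 0.82 to 0.97 against 0.73), and there is no loss at 21. The upper figure of 2.10 at 7 messages requires independent draws. All of this rests on assumed SDs, a slope of 1 and error-free pre-ratings.

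Bias between arms is a conditional risk: it needs the message mix to differ by arm. The stated power of at least 80% concerns another outcome, is reproduced, and is unaffected. The change is worth making before the data are seen. It does not call the laboratory endpoints into question.

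**What to change.** In Data Analysis & Statistical Considerations, Specific Aim 2:
- Model each phone rating in the multilevel model with group, the message's pre-rated valence as a covariate, and crossed random intercepts for participant and message.
- Report rating minus pre-rated valence (negative values meaning negative bias) as a sensitivity score. Say that it is not equivalent to the main model, because it fixes the slope at 1 while the covariate model estimates it.
- State how messages are assigned to prompts and whether all participants draw on one common set.
- State that neither score removes the selection that comes from rating messages only at high-distress prompts.

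The cost is a few sentences. The pre-ratings already exist, and no extra data collection is needed provided that the identity of the message is stored with each rating.
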